Initial treatment will occur on Day 0 (date of randomization) and Day 7. On Day 0 and Day 7, Group A (FCM) will receive a 750 mg undiluted blinded dose of IV FCM at the rate of approximately 100 mg (2 mL)/minute; Group B (placebo) will receive a blinded placebo (15 cc of normal saline) IV push at 2 mL/minute. Participants in Group A with body weight <50 kg (110 pounds) will have individual FCM doses adjusted to 15 mg/kg, not to exceed an individual dose of 750 mg, or a cumulative dose of 1500 mg per treatment cycle.

All participants will be dosed every 6 months for the duration of the trial. Participants randomized to the FCM arm will be dosed as indicated based on hemoglobin (Hgb) levels (i.e. Hgb <13.5 g/dl [females] or <15.0 g/dl [males])) and iron studies (i.e. serum ferritin <100 ng/mL or 100 to 300 ng/mL with TSAT <20%). Participants not meeting post- randomization lab criteria for blood counts and iron studies and all participants randomized to the placebo arm will be administered IV placebo at each visit.

Unblinded site personnel, responsible for preparation and administration of the FCM or Placebo, will ensure that the participant and all blinded site staff are not able to observe the preparation or administration of study treatment.

**Patient
Assessments**

Efficacy and Safety Follow-up: All participants will be followed from the time of randomization until completion of the trial. The last participant randomized will be followed for 12 months. After treatment on Day 0 and Day 7, participants will be evaluated at 3 month intervals (in person or via telephone), with additional dosing administered every 6 months as applicable (see Section 3.1). Hematology, ferritin, and transferrin saturation (TSAT) laboratory assessments will be performed in all participants, with appropriate safety evaluations, to determine if additional treatment will occur at 6 month intervals. At the conclusion of the study all participants will be assessed for the occurrence of any potential endpoint or serious adverse events. Attempts to determine Vital Status, including endpoint ascertainment, for participants who are lost to follow-up or withdrawn will be made via a search of available public records, and other appropriate investigative techniques, including the potential use of third party vendors as described in the informed consent form and in accordance with applicable regulatory requirements.

**Primary
Endpoint:**

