3.3 Schedule of Events

Study Procedures	Screening	Treatment Phase		Follow-up Phase				
		0	7±2	90 ±14 ^{a,b, l}	160-176 ^{a,b}	180±7 ^{a,b}	187 ±7 ^{a,b}	EOS ^c
Informed consent	X							
Inclusion/exclusion criteria	X	X ^j						
Demographics	X							
Targeted medical history	X							
Targeted Physical Exam		X ^j						X
Vital signs		X ^d	X ^d			X ^d	X ^d	X
Height (cm) & weight (kg)		X ^e				X ^e		
Urine or serum pregnancy test		X ^f				X ^f		X ^f
1,25 (OH) ₂ Vitamin D, 25 (OH) Vitamin D and PTH ^k		X ^k			X ^k			
Left ventricular ejection fraction	X ^g							
Randomization		X ⁿ						
Hematology laboratory	X ^{hp}	X ^h			X ^h			X ^h
Chemistry laboratory		X ^h			X ^h			X ^h
Iron indices	X ^h	X ^h			X ^h			X ^h
6 Minute Walk Test		X ^j				X ^m		
NT-proBNP	X ^h	X ^h			X ^h			X ^h
Serious Adverse Event and Clinical Endpoint Event reporting		X	X	X	X	X	X	X
Concomitant medications	X	X	X			X	X	X
IV FCM/ IV Placebo		X ⁿ	X ⁿ			X ⁱⁿ	X ⁱⁿ	

Abbreviations: EOS = End of Study; FCM = ferric carboxymaltose; IV = intravenous; NT-proBNP = N-terminal pro-brain natriuretic peptide; PTH = Parathyroid Hormone;

- a Visits will be repeated every 180 days for the duration of the study
- b At end of study, the visit should not be performed if it would occur within 30 days of the EOS visit. If the participant is prematurely discontinued from the study and completing the EOS visit, the regular 6 or 12 month visit is needed to obtain the 6MWT.
- c EOS visit for all participants will be scheduled once the last participant has reached 12 months on study and the anticipated number of outcome events (Section 8) reaches 771.
- d On study drug dosing days vital signs will be collected predose, immediately postdose, and 30 minutes postdose. Participants will be discharged from the site by the Investigator or his or her designee only if there are no significant signs or symptoms 30 minutes after the administration is completed.
- e Height assessed at Day 0 only; weight assessed at Day 0 and prior to each dosing cycle.
- f Females of childbearing potential
- g. Historical value can be used if performed within 24 months of screening visit (or 36 months if LVEF ≤30%), must be performed at least 12 weeks after major cardiac intervention-including CABG, valvular intervention, or cardiac resynchronization therapy device implantation.

- h. The method of analysis of screening laboratory values will be by a central clinical laboratory. All visits will be analyzed through a central laboratory

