6.5 End of Study Visits

End of study visits for all participants will be scheduled once the last participant has reached 12 months on study and at least 771 participants have experienced an event of cardiovascular death or hospitalization for heart failure. The participants should return to the clinic and the following will be performed by blinded study staff:

- Targeted physical exam
- Vital signs including BP and heart rate
- Blood samples for central lab hematology, chemistries, iron indices and NT-proBNP.
- Urine or serum pregnancy test (women of childbearing potential only)
- Review of concomitant medications
- Adverse event / serious adverse event assessment, including evaluation of potential endpoint events (see Section 10.2).

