8.10 Stopping Rules and Interim Analysis

A Data and Safety Monitoring Committee (DSMB), with statistical support from DCRI will review safety data, including a tally of the composite outcome events at least every 6 months (See Section 10.3). The DSMB can recommend stopping the study for safety concern at any point. In addition, one interim analysis is planned to determine if an early stopping for an overwhelming efficacy should be recommended. This analysis will be conducted after 2250 (75%) participants have been enrolled. Significance level will be set at 0.0001 for this analysis, resulting in an adjusted significance level for the final analysis of 0.0099 for the primary endpoint and 0.0499 for the first secondary endpoint, preserving the overall significance at 0.01 and 0.05, respectively. Conditional power will be estimated based on data accrued to date and presented to the DSMB. The DSMB may recommend that the study continues as planned, discontinue the study or that the trial be continued with recommended changes to the protocol. The Executive Steering Committee will determine if an increase in sample size is warranted in order that at least 771 participants will experience an event of cardiovascular death or hospitalization for heart failure.

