1.4 Sample Size and Power

The study design allows for sufficient power for both the primary and top secondary outcomes. Numerical simulations based on multivariate normal vectors ([Appendix 2](#)) were conducted to estimate power for the primary treatment comparison based on the following assumptions about events rates described in **Table 1.4.1**

Table 1.4.1. Assumptions about Event Rates for Primary Outcome

Ranked tier at 12-month endpoint (6 month for 6 MWT)	Control	Treatment
Death total	8%	6.8%
Death without hospitalization	4%	3.4%
Death with hospitalization	4%	3.4%
Hospitalizations in survivors		
1	6%	4.8%
2	3%	2.4%
3 or more	1%	0.8%
Change in 6 Minute Walk Test	Mean = 0 SD = 90	Mean = 18 SD = 90

With 3014 participants (1507 per arm) and 2.5% annual loss to follow-up for clinical outcomes and 15% of individuals with missing 6MWT at 6 months (unable to perform or lost to follow-up), projected simulations estimate 90% power at an overall two-sided significance level of 0.01, accounting for one interim analysis as described in [Section 7.1](#).

For the top secondary composite, there is an assumed event rate of 0.0128 per month in the control arm which represents conservative 75% discounting of the event rate obtained by the FCM meta-analysis [[Anker 2015](#)]. The anticipated hazard ratio (HR) was set at 0.80 (20% reduction). Uniform enrollment was assumed over the period of 30 months, with an anticipated minimum follow-up of 12 months (required minimum of 6 months), anticipated maximum follow-up of 42 months (no required maximum), and monthly loss to follow-up of 0.0021 (2.5% annualized). With these assumptions, 1500 per study arm (3000 total) provides 90% power to reject the null hypothesis of no difference between treatment arms when tested at an overall two-sided level of significance $\alpha=0.05$, accounting for one interim analysis as described in Section 8.10 of the CSP. This results in a total of 771 participants with events (in case of multiple events experienced by a participant, only their first one will be counted towards the 771) necessary to achieve the desired power. Thus, the trial has the potential opportunity to be stopped at a point where the projected number of participants reaches 771 events, but no earlier than the last participant reaching 12 months of follow-up.

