In order to maintain an overall alpha of 0.01 and account for interim analysis we will use a two-sided alpha of 0.0099 for the final analysis of the primary endpoint.

At the request of the FDA, the overall alpha for the top secondary endpoint was changed from 0.05 to 0.04. In order to maintain an overall alpha of 0.04 and account for interim analysis we will use a two-sided alpha of 0.0399 for the final analysis of the top secondary endpoint.

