5.2 Top Secondary Outcome

The top secondary outcome is defined as the time from randomization to the onset of first confirmed event in the composite CV outcome of CV-related death (any deaths confirmed as unknown are included in CV deaths) or hospitalization for heart failure.

In the unlikely event that two confirmed outcomes occur on the same day, the following hierarchy will be used to ascribe the primary component of the composite:

- CV-related death
- Hospitalization for heart failure

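### The documents word the 771-event close of follow-up in conflicting ways (experienced, anticipated, projected) and never tie the count to CEC-confirmed events, so the top secondary analysis can close below 771

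*Combined protocol and SAP*

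**What the plan says.** Four places in protocol version 3 and SAP v1.3 link the end of follow-up to 771 events for the top secondary outcome (CV death or heart failure hospitalization).

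- **Protocol 6.5** schedules end-of-study visits once the last participant has reached 12 months and "at least 771 participants have experienced an event of cardiovascular" death or heart failure hospitalization. This is an observed count.
- **Protocol 3.3, footnote c**, joins the same 12 months to the condition that "the anticipated number of outcome events (Section 8) reaches 771".
- **Protocol 8.8 and SAP 1.4** are permissive. In the SAP's wording, "the trial has the potential opportunity to be stopped at a point where the projected number of participants reaches 771 events", though not before the last participant's 12 months. SAP 1.4 adds that only a participant's first event counts.

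The paragraph in 8.8 and 1.4 that sets this 12-month floor also lists, among its planning assumptions, an "anticipated minimum follow-up of 12 months (required minimum of 6 months"). The protocol synopsis, under patient assessments, says "The last participant randomized will be followed for 12 months".

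The analysed endpoint is adjudicated. Protocol 8.5 defines the composite by adjudicated events, and SAP 5.2 measures time to "the onset of first confirmed event in the composite CV outcome".

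**The concern.** Observed, anticipated and projected counts can give different closing dates. A forecast of 771 can be wrong, and a close date set on it then leaves fewer than 771 events. Protocol 6.5 forbids that outcome; SAP 1.4 allows it. No text says which governs.

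The count also has no stated link to adjudication. Protocol 7.3 foresees suspected events that the CEC reviews and finds not to meet endpoint criteria, so the reported count can exceed the confirmed count. If reported events trigger the close, the Cox analysis of confirmed events starts short.

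The power of the top secondary comparison and the pre-specification of the closing date are both at stake.

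**Working it through.** **Inputs.** From SAP 1.4: control rate 0.0128 per month, hazard ratio 0.80 (so 0.01024 on FCM), uniform accrual over A = 30 months, minimum follow-up F = 12 months, loss η = 0.0021 per month, 1507 per arm. Final-analysis alpha was "0.0099 for the primary endpoint and 0.0499 for the first secondary endpoint" in protocol 8.10. SAP 1.4 now says "we will use a two-sided alpha of 0.0399 for the final analysis of the top secondary endpoint".

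**Step 1: reproduce 771.** The probability of an observed event in an arm with hazard λ, writing t = λ + η, is

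p = (λ/t) × {1 − [exp(−tF) − exp(−t(A+F))]/(tA)}

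- Control, t = 0.0149: 0.8591 × {1 − (0.8363 − 0.5348)/0.447} = 0.2797
- FCM, t = 0.01234: 0.8298 × {1 − (0.8624 − 0.5955)/0.3702} = 0.2317

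Expected events = 1507 × (0.2797 + 0.2317) = 770.8 with unrounded probabilities (767.2 with 1500 per arm). So 771 is the number the plan expects at month 42, when the last participant reaches 12 months. The two conditions coincide only if every assumption holds, and there is no margin.

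**Step 2: power at 771.** Unadjusted Schoenfeld: power = Φ(½√D × |ln 0.80| − z). With D = 771 the first term is 3.098.

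- Alpha 0.0499: Φ(3.098 − 1.961) = 87.2%
- Alpha 0.0399: Φ(3.098 − 2.055) = 85.2%

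The stated 90% is not reproduced. It would need 845 events at 0.0499 or 895 at 0.0399.

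**Step 3: 771 counted or projected, fewer confirmed.** The documents give no confirmation rate, so the range is assumed.

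| Confirmed | Events analysed | ½√D × \|ln 0.80\| | Power at 0.0399 | Power at 0.0499 |
|---|---|---|---|---|
| 100% | 771 | 3.098 | 85.2% | 87.2% |
| 95% | 732 | 3.020 | 83.3% | 85.5% |
| 90% | 694 | 2.939 | 81.2% | 83.6% |
| 80% | 617 | 2.771 | 76.3% | 79.1% |

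**Step 4: time to reach 771 confirmed.** I multiplied the Step 1 event count by the confirmation rate and increased F until the product reached 771. The extra follow-up beyond month 42 is about 1.7, 3.6 and 8.5 months at 95%, 90% and 80%. Just after month 42 the model adds about 24 events per month before any discount for confirmation.

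**The case against.** Protocol 6.5 is the operational instruction for scheduling the final visits. Read literally and with confirmed events, it prevents any shortfall. Protocol 8.10 and SAP 7.1 point the same way: the Executive Steering Committee may enlarge the sample so that at least 771 participants have an event. The wording in 8.8 and 1.4 offers an opportunity to stop, not an order. The CEC link can be inferred, since 771 is derived for a composite that protocol 8.5 defines as adjudicated, and footnote c points to Section 8. Events also keep accruing between the trigger and the final visits, and the calculation ignores the covariate adjustment in SAP 4.1. All of this limits the size of the problem. It does not settle which wording governs or state what is counted.

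Three stronger readings are tempting, and the documents do not support them.

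- **A close at six months.** The 12-month floor in 3.3, 6.5, 8.8 and SAP 1.4 rules it out. The six-month phrase contradicts the floor but does not override it.
- **A fixed 12-month close whatever the event count.** The synopsis sentence could suggest this. The sentences around it have everyone followed until the trial is complete, and the synopsis gives 365 days as a minimum. It is loose wording, not a separate stop rule.
- **Unconfirmed events are to be counted.** No text says so. The documents are silent on whether the count is of confirmed events.

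**Conclusion.** The concern holds as a conflict between stop rules and an undefined count. Following SAP 1.4 as written permits an analysis below 771 that protocol 6.5 does not allow, and the plan has no spare events at its earliest close. If confirmation falls short, the loss is about 2, 4 or 9 percentage points of power at 95%, 90% or 80%, starting from 85%. These figures rest on the plan's hazard ratio of 0.80, an unadjusted log-rank approximation, an assumed confirmation range, and no events added during close-out.

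The larger gap, from the stated 90% to 85%, has a different cause: 771 events give 87% at 0.0499, and the later move to 0.0399 takes off a further two points. It should not be attributed to the stopping language, but any shortfall adds to it.

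**What to change.** Put one rule in SAP 1.4 and in protocol 6.5, 8.8 and footnote c of 3.3: follow-up closes when at least 771 participants have a CEC-confirmed first CV death or heart failure hospitalization and the last participant has had at least 12 months. If the date must be set by projection, project confirmed events, for example reported first events multiplied by the running confirmation rate. Delete the parenthetical six-month minimum from 8.8 and 1.4, and reword the synopsis sentence as at least 12 months. Restate the power for 771 events at the current alpha alongside the rule.

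The cost is wording plus possible extra follow-up: about 2 to 4 months at 95% to 90% confirmation and about 8 at 80%, less whatever accrues during close-out. If nearly all counted events are confirmed, the cost is close to nil.

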1.5 Schedule of Major Assessments

Following randomization, outcomes and serious adverse event data are collected at 90 days and at every 6 monthly visit as detailed in schedule of events (Section 3.3 of the CSP)

1.6 Summary of Relevant Amendments to the Protocol

Please refer to [Appendix 1](#) for this information. The version the participant was enrolled under will be available in the database.

2 ANALYSIS SETS

2.1 Intent-to-treat (ITT) Population

The ITT population consists of all participants randomized to a treatment group in the study regardless of their compliance with the study medication. The participants are analysed in the treatment group to which they were randomized. This is the primary population of all efficacy analyses.

Any participant who gets a treatment assigned via the IXRS will be considered to have been randomized.

2.2 Safety Population

The Safety population will consist of all ITT participants who received at least 1 dose of study medication identified by the presence of injection start date. When summarizing data using this population, participants are analyzed in the As Treated group. If a participant receives any FCM study drug, then the participant will be counted as treated in the FCM arm, regardless of the amount of medication received; otherwise the participant will be counted as treated in the placebo arm.

The Safety population will be used for assessing Safety.

2.3 Per-protocol (PP) Population

The Per-Protocol Population is a subset of the ITT population excluding participants who complied with the randomized treatment for less than 50% of the dosing prior to 1 year follow-up. In cases of medication error, treatment assignments in the per-protocol analysis will be analyzed according to the actual treatment received as the first study drug dose.

2.4 Hypophosphatemia Sub-study (HS) Population

The Hypophosphatemia Sub-study (HS) population will consist of all ITT participants who enrolled in the sub-study identified by the presence of injection start date. When summarizing data using this population, participants will be analyzed according to the actual treatment received as the first dose.

The HS population will be used for assessing Safety.

Please see the HS SAP for further details.

3 BACKGROUND CHARACTERISTICS

3.1 Disposition of Participants

Disposition data will be summarized for all randomized participants. The summary by treatment will include

- Inclusion in the four study populations
- Participants completing study alive
- Lost to follow up
- Withdrawn consent for follow up
- Reason study drug permanently discontinued

3.2 Demographic and Baseline Characteristics

The demographic, baseline clinical and anthropometric characteristics collected in the study will be tabulated and summarised as descriptive statistics by treatment for both ITT and Safety populations.

3.3 Medical History

Participant medical history will be summarized within both ITT and Safety populations.

- Duration of HF calculated as (year of randomization – year of onset) +1 and etiology of HF at baseline will be summarized by treatment.

All other medical history data collected in the study will be summarized by treatment group.

4 METHODS OF ANALYSIS

4.1 General Principles

In addition to specific analyses and presentations that are detailed in the following sections, results will be summarised using descriptive statistics, including the number of participants, mean, standard deviation, median, and range as appropriate. For categorical variables, counts and percentage per treatment group will be presented.

Summaries of continuous characteristics will be based on non-missing observations. Percentage for categorical variables will be calculated based on number of participants with non-missing values for the variable.

Unless otherwise stated, timings of efficacy endpoints will be relative to the date of randomization. Specifically, for all time-to event analyses (defined as [event date – randomization date] +1 where event occurs and as [appropriate censoring date based on analytic population – randomization date] +1 where event does not occur), the treatment groups will be analysed using a Cox proportional hazards model that includes treatment as an explanatory factor, region as stratification factors along with pre-specified baseline covariates: age, sex, ejection fraction, NYHA class, heart failure etiology (Ischemic vs. non-ischemic (unknown etiology considered as non-ischemic)), NT-proBNP, haemoglobin, ferritin, TSAT, eGFR and BMI, unless specified otherwise. If any of the pre-specified baseline covariates have >5 participants with missing data, they will not be used in the analyses to maintain the ITT population for the model. If the baseline covariate is missing data on ≤ 5 participants, we will impute the missing value with overall mode if categorical covariate and the overall mean if continuous variable. The Efron method will be used for handling ties. P-value and confidence intervals for the HR will be based on the Wald statistic. Any analyses using events that are confirmed by the CEC will use the CEC adjudicated responses and related dates. Analyses of Cardiovascular (CV) death, will include deaths with cause of death confirmed as unknown. In addition, the summary tables of these analyses will include the number of participants with event and the cumulative incidence (1 – the “survival” or event-free proportion) over time per treatment group presented annually through the last time point where 90% of the overall events have occurred. Cumulative incidence function and Kaplan-Meier estimates of participants with events will also be calculated and plotted through maximum follow up available in the study, with number of participants at risk indicated below the plot at specific times.

We will present empirical cumulative distribution function curves by treatment of change in 6MWT distance at 6 and 12 months.

For all the hierarchical composite endpoints, in addition to primary analytic method, we will present win-ratio along with its confidence interval.

The timing of safety data will be relative to the study drug start date. Specifically, any time to safety event durations will be defined as [event date – study drug start date] +1 where event occurs and as [appropriate censoring date based on analytic population – study drug start date] +1 where event does not occur).

Baseline is defined as response/value collected closest to randomization and on or prior to study drug start. If both date and time are available we will use the value prior to the first study drug start date time. However, if only dates are available, we will use the values on or prior to first study drug start date as the baseline. Any measures (for example central labs) without a value in this window will have a missing baseline value.

End of study date for the participant will be driven off of the date of their final study disposition. Date of last contact for the participant will be driven off of their last visit

performed, these dates can be different from the date last known alive collected on end of study form for withdrawn consent participants.

The median and total person-years of follow-up for the whole study will also be reported.

All analyses included in this SAP will be performed using SAS v9.4 or higher. They will be based on Clinical Data Interchange Standards Consortium (CDISC) standard data (Analysis Data Model (ADaM) and/or Study Data Tabulation Model (SDTM)). The summaries will be presented as either tables or, where appropriate, as figures. International Council for Harmonisation (ICH) required listings will also be produced.

- “n” will be displayed as a whole number
- The Mean, SD, Median, Q1, and Q3 will be displayed with 1 more decimal place than the source data precision.
- The Min and Max will be displayed with the same number of decimal places as the source data. Any other presentation of raw data will be also be displayed with the same decimal places as the source data.
- All tests and confidence intervals are 2-sided unless specified otherwise.
- All p-values will be displayed with three decimal places.
- All by visit summaries and analyses will use scheduled/nominal.

